12.2 CTEP Multicenter Guidelines

N/A

12.3 Collaborative Agreements Language

The agent(s) supplied by CTEP, DCTD, NCI used in this protocol is/are provided to the NCI under a Collaborative Agreement (CRADA, CTA, CSA) between the Pharmaceutical Company(ies) (hereinafter referred to as "Collaborator(s)") and the NCI Division of Cancer Treatment and Diagnosis. Therefore, the following obligations/guidelines, in addition to the provisions in the "Intellectual Property Option to Collaborator" (http://ctep.cancer.gov/industryCollaborations2/intellectual_property.htm) contained within the terms of award, apply to the use of the Agent(s) in this study:

1. Agent(s) may not be used for any purpose outside the scope of this protocol, nor can Agent(s) be transferred or licensed to any party not participating in the clinical study. Collaborator(s) data for Agent(s) are confidential and proprietary to Collaborator(s) and shall be maintained as such by the investigators. The protocol documents for studies utilizing Agents contain confidential information and should not be shared or distributed without the permission of the NCI. If a copy of this protocol is requested by a patient or patient's family member participating on the study, the individual should sign a confidentiality agreement. A suitable model agreement can be downloaded from: <http://ctep.cancer.gov>.
2. For a clinical protocol where there is an investigational Agent used in combination with

(an)other Agent(s), each the subject of different Collaborative Agreements, the access to and use of data by each Collaborator shall be as follows (data pertaining to such combination use shall hereinafter be referred to as "Multi-Party Data"):

- a. NCI will provide all Collaborators with prior written notice regarding the existence and nature of any agreements governing their collaboration with NCI, the design of the proposed combination protocol, and the existence of any obligations that would tend to restrict NCI's participation in the proposed combination protocol.
- b. Each Collaborator shall agree to permit use of the Multi-Party Data from the clinical trial by any other Collaborator solely to the extent necessary to allow said other Collaborator to develop, obtain regulatory approval or commercialize its own Agent.
- c. Any Collaborator having the right to use the Multi-Party Data from these trials must agree in writing prior to the commencement of the trials that it will use the Multi-Party Data solely for development, regulatory approval, and commercialization of its own Agent.

3. Clinical Trial Data and Results and Raw Data developed under a Collaborative Agreement will be made available to Collaborator(s), the NCI, and the FDA, as appropriate and unless additional disclosure is required by law or court order as described in the IP Option to Collaborator (http://ctep.cancer.gov/industryCollaborations2/intellectual_property.htm). Additionally, all Clinical Data and Results and Raw Data will be collected, used and disclosed consistent with all applicable federal statutes and regulations for the protection of human subjects, including, if applicable, the *Standards for Privacy of Individually Identifiable Health Information* set forth in 45 C.F.R. Part 164.
4. When a Collaborator wishes to initiate a data request, the request should first be sent to the NCI, who will then notify the appropriate investigators (Group Chair for Cooperative Group studies, or PI for other studies) of Collaborator's wish to contact them.
5. Any data provided to Collaborator(s) for Phase 3 studies must be in accordance with the guidelines and policies of the responsible Data Monitoring Committee (DMC), if there is a DMC for this clinical trial.
6. Any manuscripts reporting the results of this clinical trial must be provided to CTEP by the Group office for Cooperative Group studies or by the principal investigator for non-Cooperative Group studies for immediate delivery to Collaborator(s) for advisory review and comment prior to submission for publication. Collaborator(s) will have 30 days from the date of receipt for review. Collaborator shall have the right to request that publication be delayed for up to an additional 30 days in order to ensure that Collaborator's confidential and proprietary data, in addition to Collaborator(s)'s intellectual property rights, are protected. Copies of abstracts must be provided to CTEP for forwarding to Collaborator(s) for courtesy review as soon as possible and preferably at least three (3) days prior to submission, but in any case, prior to presentation at the meeting or publication in the proceedings. Press releases and other media presentations must also be forwarded to CTEP prior to release.

Copies of any manuscript, abstract and/or press release/ media presentation should be sent to:

Email: [contact]

The Regulatory Affairs Branch will then distribute them to Collaborator(s). No publication, manuscript or other form of public disclosure shall contain any of Collaborator's confidential/ proprietary information.

13 STATISTICAL CONSIDERATIONS

13.1 Study Design/Endpoints

COHORT A - Study Design and Endpoints

This is a phase II two-stage clinical trial with a primary endpoint of objective response per RECISTS 1.1 among patients with advanced ULMS treated with nivolumab.

For the primary endpoint of overall response with a null hypothesis of 5% and an alternative hypothesis of 20% we would need 37 patients in a two-stage design with 12 patients in the first stage and 25 patients in the second stage. At the first stage analysis we will assess overall response, we will need to observe at least 1 response out of 12 patients to continue through the second stage. At the second stage we will assess overall response rate again, and we will need to observe at least 4 responses out of 37 patients to accept the treatment. The overall power for overall response rate is 90%. The overall type I error, the chance of incorrectly rejecting the null hypothesis is 9%. The probability of stopping at the first stage under the null hypothesis is 54%. The operating characteristics of this design are calculated using the exact binomial distribution. Subjects who continue treatment beyond initial investigator-assessed, RECIST 1.1-defined the initial progression event but may be designated as delayed responses for purposes of determining ORR and counted as responses for two stage designs.

Paired immediate pre-treatment and post- treatment biopsies will be obtained whenever possible in consenting patients, and in a minimum of 10 patients. If less than 10 patients have provided paired tumor biopsies, the remaining slots will give priority to obtain biopsies in the last group of 10 patients prior to completion of accrual. For the primary endpoint of overall response rate with the parameters as noted in section 13.1, a total sample size of 37 patients is needed in a two-stage design with 12 patients in the first stage and 25 patients in the second stage. A minimum accrual rate is expected to be 3 subjects per month. With a minimal accrual rate of 3 subjects per month, we expect the study enrollment to last approximately 13 months.

For Cohort A, 12 participants were accrued to the first stage. Since an objective response was not seen in the first stage of Cohort A, enrollment to the second stage did not begin.

COHORT B – Study Design and Endpoints

This phase II two-stage clinical trial will include patients with advanced ULMS treated with

nivolumab and ipilimumab with a primary endpoint of objective response per RECISTS 1.1 among

For the primary endpoint of overall response with a null hypothesis of 5% and an alternative hypothesis of 30% we would need 25 patients in a two-stage design with 8 patients in the first stage and 17 patients in the second stage. At the first stage analysis we will assess overall response, we will need to observe at least 1 response out of 8 patients to continue through the second stage. At the second stage, we will assess overall response rate again, and we will need to observe at least 3 responses out of 25 patients to accept the treatment. The overall power for overall response rate is 94%. The overall type I error, the chance of incorrectly rejecting the null hypothesis is 9%. The probability of stopping at the first stage under the null hypothesis is 66%. The operating characteristics of this design are calculated using the exact binomial distribution.

Subjects who continue treatment beyond initial investigator-assessed, RECIST 1.1-defined progression will be considered to have investigator-assessed progressive disease at the time of the initial progression event but may be designated as delayed responses for purposes of determining ORR and counted as responses for two stage designs.

In order to assess the impact of immune checkpoint inhibition in this population, tissue will be acquired to analyze the integrated biomarkers and determine the potential drug effect in this disease. Biomarkers will be assessed from pre-treatment and post-treatment biopsies collected in a minimum of 10 patients on this study. During enrollment to Cohort A, one set of pre-treatment and post-treatment biopsies was collected; the additional 9 were not performed because the study did not progress to Stage II. In Cohort B, paired immediate pre-treatment and post-treatment biopsies will be collected in the first eight participants who enroll to the study (stage 1-Cohort B). For this cohort, participants are required to have disease that can be biopsied safely, as discussed in Section 3.1.11. Biopsies will be optional among participants enrolled in the second stage of cohort B.

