1. OBJECTIVES

1.1 Primary Objectives

- To evaluate the objective response rate per RECIST 1.1 of patients with advanced leiomyosarcoma of the uterus (ULMS) treated with nivolumab.
- To evaluate the objective response rate per RECIST 1.1 of patients with advanced (ULMS) treated with nivolumab in combination with ipilimumab.

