11 MEASUREMENT OF EFFECT

11.1 Antitumor Effect – Solid Tumors

For the purposes of this study, patients should be re-evaluated for response every 8 weeks (+/- 2 days). In addition to a baseline scan, confirmatory scans should also be obtained at least 4 weeks following initial documentation of objective response.

Response and progression will be evaluated in this study using the new international criteria proposed by the revised Response Evaluation Criteria in Solid Tumors (RECIST) guideline (version 1.1) [Eur J Ca 45:228-247, 2009]. Changes in the largest diameter (unidimensional measurement) of the tumor lesions and the shortest diameter in the case of malignant lymph nodes are used in the RECIST criteria.

All patients who receive at least one dose of nivolumab and ipilimumab each will be included in the toxicity analysis. This includes participants who receive study drug and are ultimately deemed ineligible.

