11.1.4.3 Evaluation of Best Overall Response

The best overall response is the best response recorded from the start of the treatment until disease progression/recurrence (taking as reference for progressive disease the smallest measurements recorded since the treatment started). The patient's best response assignment will depend on the achievement of both measurement and confirmation criteria.

For Patients with Measurable Disease (*i.e.*, Target Disease)

| Target Lesions | Non-Target Lesions | New Lesions | Overall Response | Best Overall Response when Confirmation is Required* |
|----------------|-----------------------------|-------------|------------------|--|
| CR | CR | No | CR | ≥ 4 wks. Confirmation** |
| CR | Non-CR/Non-PD | No | PR | ≥ 4 wks. Confirmation** |
| CR | Not evaluated | No | PR | |
| PR | Non-CR/Non-PD/not evaluated | No | PR | |
| SD | Non-CR/Non-PD/not evaluated | No | SD | Documented at least once ≥ 4 wks. from baseline** |
| PD | Any | Yes or No | PD | no prior SD, PR or CR |
| Any | PD*** | Yes or No | PD | |
| Any | Any | Yes | PD | |

* See RECIST 1.1 manuscript for further details on what is evidence of a new lesion.

** Only for non-randomized trials with response as primary endpoint.

*** In exceptional circumstances, unequivocal progression in non-target lesions may be accepted as disease progression.

Note: Patients with a global deterioration of health status requiring discontinuation of treatment without objective evidence of disease progression at that time should be reported as “*symptomatic deterioration*.” Every effort should be made to document the objective progression even after discontinuation of treatment.

For Patients with Non-Measurable Disease (*i.e.*, Non-Target Disease)

| Non-Target Lesions | New Lesions | Overall Response |
|--------------------|-------------|------------------|
|--------------------|-------------|------------------|

| | | |
|-------------------|-----------|----------------|
| CR | No | CR |
| Non-CR/non-PD | No | Non-CR/non-PD* |
| Not all evaluated | No | not evaluated |
| Unequivocal PD | Yes or No | PD |
| Any | Yes | PD |

* 'Non-CR/non-PD' is preferred over 'stable disease' for non-target disease since SD is increasingly used as an endpoint for assessment of efficacy in some trials so to assign this category when no lesions can be measured is not advised

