13.6.2 Evaluation of Response

All eligible patients included in the study must be assessed for response to treatment, even if there are major protocol treatment deviations or if they are ineligible. Each patient will be assigned one of the following categories: 1) complete response, 2) partial response, 3) stable disease, 4) progressive disease, 5) early death from malignant disease, 6) early death from toxicity, 7) early death because of other cause, or 9) unknown (not assessable, insufficient data). [Note: By arbitrary convention, category 9 usually designates the “unknown” status of any type of data in a clinical database.]

All of the patients who met the eligibility criteria (with the possible exception of those who received no study medication) should be included in the main analysis of the response rate. Patients in response categories 4-9 should be considered to have a treatment failure (disease progression). Thus, an incorrect treatment schedule or drug administration does not result in exclusion from the analysis of the response rate. Precise definitions for categories 4-9 will be protocol specific.

All conclusions should be based on all eligible patients. Subanalyses may then be performed on the basis of a subset of patients, excluding those for whom major protocol deviations have been identified (e.g., early death due to other reasons, early discontinuation of treatment, major protocol violations, etc.). However, these subanalyses may not serve as the basis for drawing conclusions concerning treatment efficacy, and the reasons for excluding patients from the analysis should be clearly reported. The 95% confidence intervals should also be provided.

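### Cohort B's RECIST 1.1 response count can include patients already recorded as RECIST 1.1 progressive, with no stated rule for making that call

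*Combined protocol and SAP*

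**What the plan says.** Section 1.1 gives the Cohort B objective: "To evaluate the objective response rate per RECIST 1.1 of patients with advanced (ULMS) treated with nivolumab in combination with ipilimumab". Section 13.1 repeats the RECIST 1.1 label and sets the hypotheses: "For the primary endpoint of overall response with a null hypothesis of 5% and an alternative hypothesis of 30" percent. Stage 2 opens with at least 1 response in 8, and the regimen is accepted with at least 3 in 25. The stated type I error is 9%, power 94%, and early stopping under the null 66%.

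The next paragraph of 13.1 says that patients who continue treatment past RECIST 1.1 progression "will be considered to have investigator-assessed progressive disease at the time of the initial progression event" and yet "may be designated as delayed responses for purposes of determining ORR and counted as responses for two stage designs".

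Two other sections bear on the same patients:
- 11.1.4.3: "The best overall response is the best response recorded from the start of the treatment until disease progression/recurrence".
- 13.6.2, on the main response analysis, where category 4 is progressive disease: "Patients in response categories 4-9 should be considered to have a treatment failure (disease progression"). It adds: "Precise definitions for categories 4-9 will be protocol specific".

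**The concern.** The count that drives both decisions has two incompatible definitions. Under 11.1.4.3 and 13.6.2, a patient who progresses and later shrinks is a failure. Under 13.1 she may be a responder. An analyst cannot apply both, and the verb in 13.1 is permissive, so two analysts following the protocol could report different response counts from the same scans.

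The thresholds make this consequential. With no other response among the first 8, one designation is the difference between closing the cohort and enrolling up to 17 more patients. At the end, one patient can separate 2 of 25 from 3 of 25. Either decision would be reported under a RECIST 1.1 label.

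**Working it through.** **1. Reproduce the stated design figures.** Inputs from 13.1: first stage 8, second stage 17, continue with at least 1 response, accept with at least 3 in total, null 5%, alternative 30%.

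P(stop early) = (1 − p)^8. At p = 0.05 this is 0.95^8 = 0.6634.

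P(accept) = Σ over x from 1 to 8 of P(X1 = x) × P(X2 ≥ 3 − x), with X1 ~ Bin(8, p) and X2 ~ Bin(17, p).

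At p = 0.05:
- x = 1: 0.2793 × 0.2078 = 0.0580
- x = 2: 0.0515 × 0.5819 = 0.0299
- x ≥ 3: 0.0058 × 1 = 0.0058
- Sum: 0.0938

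At p = 0.30: 0.1977 × 0.9807 + 0.2965 × 0.9977 + 0.4482 = 0.9379.

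These round to the stated 66%, 9% and 94%. The design arithmetic is right.

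**2. Follow one patient through the text.** Suppose none of the first 8 responds before progression, and one patient progresses, stays on treatment under 5.9, and later falls at least 30% below her baseline sum.

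| Section | Status | Stage 1 count |
|---|---|---|
| 11.1.4.3 | best response recorded only up to progression | 0 of 8, stop |
| 13.6.2 | category 4, failure | 0 of 8, stop |
| 13.1 | may be called a delayed response | 1 of 8, continue |

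On the third row, acceptance then needs 2 more responses in 17, which has probability 0.2078 at p = 0.05.

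**3. Look for a rule governing the call.**
- 11.1.4.1 defines partial response as a 30% decrease in the target-lesion sum from baseline. It does not say how lesions that appeared at progression enter a later response.
- 11.1 says that "confirmatory scans should also be obtained at least 4 weeks following initial documentation of objective response". Nothing applies this to a response after progression.
- 5.9 says who may continue treatment, when a new lesion is measurable and may enter the tumor burden, and how progression is dated. It does not define a response.
- 11.1.7 sends only RECIST PR or CR to the imaging core, and only at study completion, which is after the stage 1 decision.
- 12.1 requires the Protocol Principal Investigator and the Protocol Statistician to sign off before stage 2. It does not say who designates an individual delayed response.

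**4. Illustrate the size under each reading of the null.** The documents do not say whether the 5% includes delayed responses. If it does, P(accept) under the null stays at 9.4%. If it does not, and delayed responses add d percentage points, the formula in step 1 applies at p = 5% + d:

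| Assumed d (points) | P(open stage 2) | P(accept) |
|---|---|---|
| 0 | 33.7% | 9.4% |
| 0.25 | 35.0% | 10.5% |
| 0.5 | 36.4% | 11.6% |
| 1 | 39.0% | 13.9% |
| 2 | 44.0% | 19.1% |
| 3 | 48.7% | 24.6% |

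Every d is an assumption; the documents give no delayed-response rate.

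**The case against.** The strongest reply is that 13.1 is the trial-specific rule and states two purposes on purpose: the patient is dated as progressive when she progresses, and she may still count toward ORR. Section 2.2.1 gives the reason, since responses to this drug class may be delayed or follow radiographic progression. Section 13.6.2 leaves its category definitions to the protocol. This stands as a defense of counting delayed responses. It does not remove the conflict with the RECIST 1.1 label or with the best-response window in 11.1.4.3, and no section supplies the redefinition that 13.6.2 allows for.

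A second reply is that discretion is bounded. Section 5.9 limits the pool to progression in the first 24 weeks, with at most 4 new lesions, a 40% limit tied to the initial sum including new lesions, and a clinically stable patient whom the investigator judges to benefit. Opening stage 2 needs two signatures. A reader might infer that one investigator could open stage 2 unchecked; section 12.1 does not support that. These limits still govern continuation and go/no-go, not how a response is called.

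A third reply is that the null and the count describe the same quantity, because 13.1 sets the null for overall response and then counts delayed responses in ORR. That is a reasonable reading, and under it the 9% stands. A range of 1 to 3 points would also be generous: on a 5% base it means 1 in 6 to 3 in 8 of all counted responses are delayed. The smaller values are shown for that reason.

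**Conclusion.** The primary endpoint has a real definitional fault that should be fixed before the stage 1 analysis. The stated rules give contradictory counts for the same patient, and the permissive rule in 13.1 has no stated criteria, confirmation requirement or decision-maker. This conclusion rests on the text alone and needs no assumed rate.

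A reader might infer that the 9% type I error is wrong. The documents do not support that. It is exact for a count with a 5% null, and inflation requires both that the null excludes delayed responses and that they occur at some rate; neither is stated. The 10.5% to 24.6% range is illustration only. If the null includes delayed responses, the error rate holds and the fault is the RECIST 1.1 label.

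A reader might also infer that delayed responses have to be dropped from the stage rules. The plan's rationale makes that a choice for the sponsor. Nor does Cohort A settle the rate: no response in 12 patients on nivolumab alone is compatible with a wide range (one-sided 95% upper limit 1 − 0.05^(1/12) = 22.1%) and concerns a different regimen.

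**What to change.** Before the stage 1 analysis, reconcile sections 1.1, 11.1.4.3, 11.1.7, 13.1 and 13.6.2:
- Replace the permissive wording in 13.1 with a fixed rule built from the protocol's own criteria: at least a 30% decrease from the baseline sum with new lesions included, confirmed at 4 weeks or more, and called by a named existing role.
- State that the 5% null refers to that count.
- Label the endpoint accordingly in 1.1 and 13.1, and bring the best-response window, the failure categories and the scope of imaging-core review into line.
- Report alongside it the strict RECIST 1.1 ORR (confirmed CR or PR before first progression) and the decision it would have given at each stage.

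The cost is wording in those sections, with no added patients; confirmatory scans are already called for in 11.1.

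The sponsor could instead base both stage rules on strict RECIST 1.1 and report delayed responses descriptively. The cost is that a true delayed response would not count toward go/no-go. If the 30% alternative included an assumed 1, 2 or 3 points of delayed response, power would fall from 93.8% to 93.0%, 92.0% or 91.0% (the same formula at p = 0.29, 0.28 and 0.27).

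Neither option changes who may stay on treatment under 5.9.
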